6.8.2. Medical History

Medical histories are defined as the conditions and events recorded on the *Medical History* electronic CRF (eCRF) and the *Adverse Event* eCRF from the parent study (including ongoing conditions and events that occur before the date of the first injection in Study KGAA and continue during Study KGAA) for patients with a parent study. For patients enrolling directly per the Protocol KGAA Addendum 1.1, medical histories include the conditions and events on the

^a For patients enrolled in Study KGAA directly per Protocol Addendum 1.1, baseline will be the Study KGAA baseline.

KGAA *Medical History* eCRF and the conditions/events on the KGAA *Adverse Event* eCRF that occur before the date of the first injection in Study KGAA. If a medical history event worsens in severity or has a recurrence on or after the date of the first injection in Study KGAA, it will be recorded as an AE on the KGAA *Adverse Event* eCRF with the date of worsening or recurrence as the start date and will be considered as an AE.

The number and percentage of patients with medical histories will be summarized by treatment group for the overall mITT population and by age group using the MedDRA preferred term (PT) nested within system organ class (SOC).

The number and percentage of patients with specific medical history events of interest prespecified on the *History Assessment* eCRF (hand dermatitis, facial dermatitis, conjunctivitis, herpes zoster, and others), from the parent study for patients with a parent study and from Study KGAA for patients enrolling directly per Protocol KGAA Addendum 1.1, will be summarized by treatment group for the mITT population overall and by age group within the mITT Population.

6.9. Treatment Compliance

Treatment compliance with the investigational product will be summarized for patients who receive at least one confirmed dose of lebrikizumab for the Modified Safety Population in the Study KGAA treatment period. Treatment compliance for each patient will be calculated as:

$$Treatment\ compliance\ (\%) = 100\ \times \frac{Total\ number\ of\ injections\ administered}{Total\ number\ of\ injections\ expected}$$

- The total number of injections expected can be derived from the interactive web response system study drug dispense dataset.
- The total number of injections administered will be based on the *Study Drug Administration* eCRF page and on the prompt "Did you or a caregiver successfully inject the study drug?" in the *Dosing Diary* and *Dosing Diary Paper*.

A patient will be considered compliant if the patient received ≥75% of the expected number of injections while enrolled in the study. Descriptive statistics for percent compliance will be summarized. Sub-intervals of interest, such as compliance between visits, may also be presented.

6.10. Prior and Concomitant Therapy

Medications will be classified into anatomical therapeutic chemical (ATC) drug classes using the latest version of the World Health Organization (WHO) drug dictionary. Medication start and stop dates will be compared to the date of first dose of treatment in Study KGAA to be classified as prior or concomitant.

Prior medications are those medications that start and stop prior to the date of first dose of study treatment in Study KGAA. *Concomitant medications* are those medications that start before, on, or after the first day of Study KGAA treatment and continue into the treatment period.

Prior medication and concomitant medication will be summarized by the treatment group for the mITT Population.

Specific AD treatment used during the Study KGAA treatment period will be presented by the treatment group for the mITT Population. This will include: topical AD treatment (including TCS, TCI, and crisaborole) and systemic AD treatment (including systemic corticosteroids, immunosuppressants, biologics, and phototherapy). The TCS will be presented by potency. A definition of rescue medications is provided in Appendix 2. For patients coming from parent Study KGAD, daily TCS/TCI use will continue to be collected via patient diary until Week 52 and will be summarized.

Flare

Disease flares will be assessed based on rescue therapy usage. Flare is defined as the initiation or intensification of rescue therapy. A summary of the percentage of patients rescued by visit will be provided.

6.11. Efficacy Analyses

Table KGAA.6.6 includes the description and derivation of the efficacy/health outcomes, measures, and endpoints.

Table KGAA.6.7 provides the detailed analyses including analysis type, method and imputation, population, time point, and treatment comparisons for efficacy/health outcomes analyses.

For categorical parameters, the number and percentage of patients in each category will be presented. For continuous parameters, descriptive statistics will include n (number of patients), mean, standard deviation, median, minimum and maximum.

The Investigator's Global Assessment, EASI, and BSA will be reported by clinic visit. Pruritus NRS, Sleep-loss, POEM, and Skin-pain NRS will be summarized by the time points described in Appendix 1.

For patients with a parent study, the parent study baseline is used as the baseline for efficacy endpoints. Patients enrolled directly into Protocol KGAA Addendum 1.1 do not have a parent study, so the data collected at addendum Baseline Visit 1 will be used as a baseline for all efficacy assessments. More details are available in Section 6.1.2.

 Table KGAA.6.6.
 Description and Derivation of Efficacy/Health Outcomes Measures and Endpoints

Measure	Description	Variable	Derivation / Comment	Definition of Missing
IGA	The IGA is a static assessment and rates the severity of the patient's AD. The IGA is comprised of a 5-point scale ranging from 0 (clear) to 4 (severe) and a score is selected using descriptors that best describe the overall appearance of the lesions at a given time point.	• IGA (0,1) ^a • IGA (0)	Single item. Range: 0 to 4 0 represents "clear" 4 represents "severe" Observed score of 0 or 1 Observed score of 0	Single item, missing if missing. Single item, missing if missing.
EASI	The EASI scoring system uses a defined process to grade the severity of the signs of eczema and the extent affected. The extent of disease (percentage of skin affected: 0 = 0%; 1 = 1-9%; 2 = 10-29%; 3 = 30-49%; 4 = 50-69%; 5 = 70-89%; 6 = 90-100%) and the severity of 4 clinical signs (erythema, edema/papulation, excoriation, and lichenification) each on a scale of 0 to 3 (0 = none, absent; 1 = mild; 2 = moderate; 3 = severe) at 4 body sites (head and neck, trunk, upper limbs, and lower limbs). Half scores are allowed between severities 1, 2, and 3. Each body site will have a score that ranges from 0 to 72, and the final EASI score	EASI score	Derive EASI region score for each of the head and neck, trunk, upper limbs, and lower limbs as follows: EASI _{region} = (Erythema + edema/papulation + Excoriation + Lichenification) *(value from percentage involvement), where erythema, edema/papulation, excoriation, and lichenification are evaluated on a scale of 0 to 3 and value from percentage involvement is on a scale of 0 to 6. The total EASI score is as follows: EASI = 0.1*EASI _{head and neck} + 0.3*EASI _{trunk} + 0.2*EASI _{upper limbs} + 0.4*EASI _{lower limbs}	N/A – partial assessments cannot be saved.
	will be obtained by weight-averaging these 4 scores. Hence, the final EASI score will range from 0 to 72 for each time point.	 Change from baseline in EASI score Percent change from baseline EASI score 	Change from baseline: observed EASI score – baseline EASI score % Change from baseline: $100 \times \frac{Observed\ score - Baseline}{Baseline}$	Missing if baseline or observed value is missing.

Measure	Description	Variable	Derivation / Comment	Definition of Missing
EASI	The EASI scoring system uses a defined process to grade the severity of the signs of eczema and the extent	EASI-50	% Improvement in EASI score from baseline ≥ 50%: % Change from baseline ≤ -50	Missing if baseline or observed value is missing.
	affected. The extent of disease (percentage of skin affected: 0 = 0%; 1 = 1-9%; 2 = 10-29%; 3 = 30-49%; 4 =	EASI-75 ^a	% Improvement in EASI score from baseline ≥75%: % Change from baseline ≤-75	Missing if baseline or observed value is missing.
	50-69%; 5 = 70-89%; 6 = 90-100%) and the severity of 4 clinical signs (erythema, edema/papulation, excoriation, and lichenification) each on a scale of 0 to 3 (0 = none, absent; 1 = mild; 2 = moderate; 3 = severe) at 4 body sites (head and neck, trunk, upper limbs, and lower limbs). Half scores are allowed between severities 1, 2, and 3. Each body site will have a score that ranges from 0 to 72, and the final EASI score will be obtained by weight-averaging these 4 scores. Hence, the final EASI score will range from 0 to 72 for each time point.	EASI-90	% Improvement in EASI score from baseline ≥90%: % Change from baseline ≤-90	Missing if baseline or observed value is missing.

Measure	Description	Variable	Derivation / Comment	Definition of Missing
BSA Affected by AD	The BSA assessment estimates the extent of disease or skin involvement with respect to AD and is expressed as a percentage of the total body surface. BSA will be determined by the Investigator or designee using the patient palm = 1% rule	BSA score Change from baseline in BSA score	$BSA\ Total = BSA_{head\ and\ neck} + BSA_{trunk} + BSA_{upper\ extremities} + \\ BSA_{lower\ extremities}$ Change from baseline: observed BSA score – baseline BSA score	N/A – partial assessments cannot be saved. Missing if baseline or observed value is missing.
Skin Pain NRS ^d	Skin Pain NRS is a patient- administered, validated, 11- point horizontal scale anchored at 0 and 10, with 0 representing "no pain" and 10 representing "worst pain imaginable."	Skin Pain NRS prorated weekly mean score	The prorated weekly mean is based on the previous 7 days. If the patient has at least one daily score, the weekly mean is the prorated average of daily scores within the given week. Single item; range 0-10. eDiary data are mapped to timepoint per Appendix 1.	Weekly mean score missing if the patient has no Skin Pain NRS responses within the week.
	Overall severity of a patient's skin pain is indicated by selecting the number that best describes the worst level of skin pain in the past 24 hours. Assessments will be recorded daily by the patient using an electronic diary.	Change from baseline in Skin Pain NRS prorated weekly mean score Percent change from baseline in Skin Pain NRS prorated weekly mean score	 Change from baseline: observed Skin Pain prorated weekly mean score – baseline Skin Pain weekly mean score % Change from baseline: 100 × Observed score – Baseline Baseline 	Missing if baseline or observed value is missing.

Measure	Description	Variable	Derivation / Comment	Definition of Missing
Skin Pain NRS ^d	Skin Pain NRS is a patient-administered, validated, 11-point horizontal scale anchored at 0 and 10, with 0 representing "no pain" and 10 representing "worst pain imaginable." Overall severity of a patient's skin pain is indicated by selecting the number that best describes the worst level of skin pain in the past 24 hours. Assessments will be recorded daily by the patient using an electronic diary.	4-point improvement in Skin Pain NRS weekly mean score	Change from baseline in Skin Pain NRS prorated weekly mean score ≤-4	Missing if baseline is missing or observed value is missing.
Pruritus NRS ^b	The Pruritus NRS is an 11-point scale used by patients to rate their worst itch severity over the past 24 hours with 0 indicating "No itch" and 10 indicating "Worst itch imaginable." Assessments will be recorded daily by the patient using an electronic	Pruritus NRS prorated weekly mean score	The prorated weekly mean is based on the previous 7 days. If the patient has at least one daily score, the weekly mean is the prorated average of daily scores within the given week. Single item; range 0-10. eDiary data are mapped to timepoint per Appendix 1.	Weekly mean score missing if the patient has no Pruritus-NRS responses within the week.
	diary.	Change from baseline in Pruritus NRS prorated weekly mean score Percent change from baseline in Pruritus NRS prorated weekly mean score	Change from baseline: observed Pruritus prorated weekly mean score – baseline Pruritus weekly mean score % Change from baseline:	Missing if baseline or observed value is missing.

Measure	Description	Variable	Derivation / Comment	Definition of Missing
Pruritus NRS ^b	The Pruritus NRS is an 11-point scale used by patients to rate their worst itch severity over the past 24 hours with 0 indicating "No itch" and 10 indicating "Worst itch imaginable." Assessments will be recorded daily by the patient using an electronic diary.	4-point improvement in Pruritus NRS prorated weekly mean score	Change from baseline in Pruritus NRS weekly mean score ≤-4	Missing if baseline is missing or observed value is missing.
Sleep-loss due to pruritus ^b	Sleep-loss due to pruritus will be assessed by the patient. Patients rate their sleep	Sleep-loss prorated weekly mean score	The prorated weekly mean is based on the previous 7 days. If the patient has at least one daily score, the weekly mean is the prorated average of daily scores within the given week. Single item; range 0 - 4. eDiary data are mapped to timepoint per Appendix 1.	Weekly mean score missing if the patient has no Sleep-loss score responses within the week.
	based on a 5-point Likert scale (0 [not at all] to 4 [unable to sleep at all]). Assessments will be recorded daily by the patient using an electronic diary.	Change from baseline in Sleeploss prorated weekly mean score Percent change from baseline in Sleep-loss prorated weekly mean score	Change from baseline: observed sleep loss prorated weekly mean score – baseline sleep loss score % Change from baseline: 100 × Observed score – Baseline Baseline	Missing if baseline or observed value is missing.
		2-point improvement in Sleep-loss prorated weekly mean score	Change from baseline in Sleep-loss weekly mean score ≤-2	Missing if baseline is missing or observed value is missing.

Measure	Description	Variable	Derivation / Comment	Definition of Missing
POEM ^b	The POEM is a 7-item, validated,	POEM score	POEM total score: sum of questions 1 to 7,	If a single question is left
	questionnaire used by the patient to		Range 0 to 28.	unanswered, then that
	assess disease symptoms over the last			question is scored as 0. If
	week. The patient is asked to respond			more than one question
	to 7 questions on skin dryness,			is unanswered, then the
	itching, flaking, cracking, sleep loss,			tool is not scored. If
	bleeding, and weeping. All 7 answers			more than one response
	carry equal weight with a total			is selected, then the
	possible score from 0 to 28 (answers			response with the highest
	scored as: No days=0; $1-2$ days = 1;			score is used.
	3-4 days = 2; $5-6 days = 3$; everyday	Change from baseline	Change from baseline: observed POEM	Missing if baseline or
	= 4). A high score is indicative of a	in POEM score	score – baseline POEM score	observed value is
	poor quality of life. POEM responses			missing.
	will be captured using an electronic	4-point improvement	Change from baseline ≤-4	Missing if baseline is
	diary and transferred into the clinical	_		missing or observed
	database.			value is missing.

Abbreviations: AD = atopic dermatitis; BAS = Body Surface Area; EASI = Eczema Area and Severity Index; IGA = Investigator's Global Assessment; N/A = not applicable; NRS = Numeric Rating Scale; POEM = Patient Oriented Eczema Measure; TCI = Topical Calcineurin Inhibitors; TCS = Topical corticosteroids.

- a Secondary endpoints.
- b Daily pruritus, sleep-loss, and weekly/in-office POEM were only collected for patients participating in Studies KGAB, KGAC, KGAD, and KGAK.
- c TCS/TCI data, only collected for patients participating in Study KGAD.
- d Daily Skin-pain NRS only collected for patients participating in Study KGAK.

 Table KGAA.6.7.
 Description of Efficacy/Health Outcome Analyses

			Population		
Measure	Variable	Analysis Method	(Section 6.1.1)	Time Point	Analysis Type
IGA	Proportion of patients	Descriptive analysis	mITT	All scheduled visits in the	Secondary analysis
	achieving IGA (0,1)	with MCMC-MI ^a		Treatment Period at which scales	
				are collected	
	Proportion of patients	Descriptive analysis	mITT	All scheduled visits in the	Supplementary analysis
	achieving IGA (0)	with As Observed		Treatment Period at which scales	
				are collected	
		Descriptive analysis	mITT	All scheduled visits in the	Supplementary analysis
		with LOCF		Treatment Period at which scales	
				are collected	
EASI	Change from baseline in EASI	Descriptive analysis	mITT	All scheduled visits in the	Secondary analysis
	score	with MCMC-MI ^a		Treatment Period at which scales	
				are collected	
	Percent change from baseline	Descriptive analysis	mITT	All scheduled visits in the	Supplementary analysis
	in EASI score	with As Observed		Treatment Period at which scales	
				are collected	
		Descriptive analysis	mITT	All scheduled visits in the	Supplementary analysis
		with LOCF		Treatment Period at which scales	
				are collected	
	Proportion of patients	Descriptive analysis	mITT	All scheduled visits in the	Secondary analysis
	achieving EASI-75	with MCMC-MI ^a		Treatment Period at which scales	
				are collected	
	Proportion of patients	Descriptive analysis	mITT	All scheduled visits in the	Supplementary analysis
	achieving EASI-90	with As Observed		Treatment Period at which scales	
				are collected	
	Proportion of patients	Descriptive analysis	mITT	All scheduled visits in the	Supplementary analysis
	achieving EASI-50	with LOCF		Treatment Period at which scales	
				are collected	

Description of Efficacy/Health Outcome Analyses

			Population		
Measure	Variable	Analysis Method	(Section 6.1.1)	Time Point	Analysis Type
BSA Affected Change score	Change from baseline in BSA score	Descriptive analysis with As Observed	mITT	All scheduled visits in the Treatment Period at which scales are collected	Secondary analysis
		Descriptive analysis with LOCF	mITT	All scheduled visits in the Treatment Period at which scales are collected	Supplementary analysis
Pruritus NRS	ruritus NRS Change from baseline in Pruritus NRS	Descriptive analysis with MCMC-MI ^a	mITT	All scheduled visits in the Treatment Period at which scales are collected	Secondary analysis
Percent Change from in Pruritus NRS	Percent Change from baseline in Pruritus NRS	Descriptive analysis with As Observed	mITT	All scheduled visits in the Treatment Period at which scales are collected	Supplementary analysis
		Descriptive analysis with LOCF	mITT	All scheduled visits in the Treatment Period at which scales are collected	Supplementary analysis
	Proportion of patients achieving at least a 4-point improvement in pruritus NRS in patients who had baseline	Descriptive analysis with MCMC-MI ^a	mITT patients with baseline pruritus NRS ≥4	All scheduled visits in the Treatment Period at which scales are collected	Secondary analysis
_	pruritus NRS ≥4	Descriptive analysis with As Observed	mITT patients with baseline pruritus NRS ≥4	All scheduled visits in the Treatment Period at which scales are collected	Supplementary analysis
		Descriptive analysis with LOCF	mITT patients with baseline pruritus NRS ≥4	All scheduled visits in the Treatment Period at which scales are collected	Supplementary analysis

Description of Efficacy/Health Outcome Analyses

			Population		
Measure	Variable	Analysis Method	(Section 6.1.1)	Time Point	Analysis Type
Sleep-loss Score	Percent Change from baseline in Sleep-loss Score	Descriptive analysis with MCMC-MI ^a	mITT	All scheduled visits in the Treatment Period at which scales are collected	Secondary analysis
	Change from baseline in Sleep-loss Score Proportion of patients achieving at least 2-point improvement sleep-loss in	Descriptive analysis with As Observed	mITT	All scheduled visits in the Treatment Period at which scales are collected	Supplementary analysis
		Descriptive analysis with LOCF	mITT	All scheduled visits in the Treatment Period at which scales are collected	Supplementary analysis
		Descriptive analysis with MCMC-MI ^a	mITT patients with baseline Sleep-loss ≥ 2	All scheduled visits in the Treatment Period at which scales are collected	Secondary analysis
	patients who had baseline Sleep-loss ≥ 2	Descriptive analysis with As Observed	mITT patients with baseline Sleep-loss ≥ 2	All scheduled visits in the Treatment Period at which scales are collected	Supplementary analysis
		Descriptive analysis with LOCF	mITT patients with baseline Sleep-loss ≥ 2	All scheduled visits in the Treatment Period at which scales are collected	Supplementary analysis
Skin Pain NRS	Percent Change from baseline in Skin Pain Score	Descriptive analysis with MCMC-MI ^a	mITT	All scheduled visits in the Treatment Period at which scales are collected	Secondary analysis
	Change from baseline in Skin Pain Score	Descriptive analysis with As Observed	mITT	All scheduled visits in the Treatment Period at which scales are collected	Supplementary analysis
		Descriptive analysis with LOCF	mITT	All scheduled visits in the Treatment Period at which scales are collected	Supplementary analysis

Description of Efficacy/Health Outcome Analyses

			Population		
Measure	Variable	Analysis Method	(Section 6.1.1)	Time Point	Analysis Type
Skin Pain NRS	Proportion of patients	Descriptive analysis	mITT patients	All scheduled visits in the	Secondary analysis
	achieving at least a 4-point	with MCMC-MI ^a	with baseline	Treatment Period at which scales	
	improvement in Skin Pain		Skin Pain NRS	are collected	
	NRS in patients who had		≥4		
	baseline Skin Pain NRS ≥4	Descriptive analysis	mITT patients	All scheduled visits in the	Supplementary analysis
		with As Observed	with baseline	Treatment Period at which scales	
			Skin Pain NRS	are collected	
			≥4		
		Descriptive analysis	mITT patients	All scheduled visits in the	Supplementary analysis
		with LOCF	with baseline	Treatment Period at which scales	
			Skin Pain NRS	are collected	
			≥4		
POEM	Change from baseline in	Descriptive analysis	mITT	All scheduled visits in the	Secondary analysis
	POEM score	with As Observed		Treatment Period at which scales	
				are collected	
		Descriptive analysis	mITT	All scheduled visits in the	Supplementary analysis
		with LOCF		Treatment Period at which scales	
				are collected	

Abbreviations: AD = atopic dermatitis; BSA = body surface area; EASI = Eczema Area and Severity Index; IGA = Investigator Global Assessment; ITT = intent-to-treat; LOCF = last observation carried forward; MCMC-MI = Markov chain Monte Carlo multiple imputation; NRS = Numeric Rating Scale; POEM = Patient Oriented Eczema Measure.

a MCMC-MI will be implemented for the following two analysis groups only: 1. Patients coming from parent study KGAD (DRM06-AD06) who were lebrikizumab Q2W responders in KGAD and then were randomized in KGAA, by treatment group in KGAA; 2. Patients coming from parent studies KGAB (DRM06-AD04) and KGAC (DRM06-AD05), received lebrikizumab 250 mg Q2W during the parent study induction period and received lebrikizumab 250 mg Q2W or lebrikizumab 250 mg Q4W during the maintenance period and not in escape arm.

6.12. Health Outcomes/Quality-of-Life Analyses

The POEM is described in Table KGAA.6.6.

6.13. Bioanalytical and Pharmacokinetic/Pharmacodynamic Methods

Details of the pharmacokinetic (PK)/pharmacodynamic (PD) analyses can be found in a separate PK/PD analysis plan.

6.14. Safety Analyses

For the purposes of Study KGAA alone, the following are planned:

- listing of SAEs
- listing of AEs leading to permanent discontinuation of study drug
- summary of SAEs, and
- summary of AEs leading to permanent discontinuation of study drug.

The data will be pooled by treatment, 250 mg lebrikizumab Q2W, 250 mg lebrikizumab Q4W, and 250 mg lebrikizumab overall.

All summaries will be based on the Modified Safety Population. These analysis populations are fully defined in Section 6.1.1. A treatment emergent adverse event (TEAE) is defined as an event that first occurred or worsened in severity after the date of the first injection in Study KGAA/AD07 and on or prior to the date of the last visit within the treatment period. A listing of AEs of patients from Site CCI and Site CCI will be provided.

Listings of all the patients with AEs from the safety follow-up period will be provided.

For patients enrolled from parent studies, SAEs that occur on or after the date of first visit to Study KGAA will be reported. For patients who enrolled directly into Study KGAA per Protocol Addendum 1.1, SAEs that occur on or after the date of informed consent will be reported.

The safety data from this study, such as AEs, vital signs, and laboratory data will be used as part of integrated safety assessments and ongoing safety review through study end.

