6.20. Clinical Trial Registry Analyses

Additional analyses will be performed (if not already available from the study CSR) to fulfill the Clinical Trial Registry (CTR) requirements.

Analyses provided for the CTR requirements include the following:

Summary of AEs, provided as a dataset, will be converted to an XML file. Both SAEs and 'Other' AEs are summarized: by treatment group, by MedDRA PT.

• An AE is considered 'Serious' whether or not it is a TEAE.

- An AE is considered in the 'Other' category if it is both a TEAE and is not serious. For each SAE and 'Other' AE, for each term and treatment group, the following are provided:
 - o the number of patients at risk of an event,
 - o the number of patients who experienced each event term, and
 - o the number of events experienced.
- Consistent with www.ClinicalTrials.gov requirements, 'Other' AEs that occur in fewer than 5% of patients/subjects in every treatment group may not be included if a 5% threshold is chosen (5% is the minimum threshold).
- AE reporting is consistent with other document disclosures, for example, the CSR, manuscripts, and so forth.

7. Unblinding Plan

Unblinding details are specified in a separate unblinding plan.

8. References

- [CDC] Centers for Disease Control and Prevention. Growth Chart Training resources page. Accessed June 09, 2020. https://www.cdc.gov/nccdphp/dnpao/growthcharts/resources/sas.htm
- PhUSE resources page. Analyses and Displays Associated with Measures of Central Tendency Focus on Vital Sign, Electrocardiogram, and Laboratory Analyte Measurements in Phase 2-4 Clinical Trials and Integrated Submission Documents. 2013. Accessed June 09, 2020. http://www.phusewiki.org/docs/CSS%20White%20Papers%202016/CSS_WhitePaper_Central Tendency v1.0.pdf
- PhUSE resources page. Analyses and Displays Associated with Outliers or Shifts from Normal to Abnormal Focus on Vital Sign, Electrocardiogram, and Laboratory Analyte Measurements in Phase 2-4 Clinical Trials and Integrated Submission Documents. 2015. Accessed June 09, 2020. http://www.phusewiki.org/docs/CSS%20White%20Papers%202016/CS_WhitePaper_Outliers Shifts_v1.0.pdf

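### The TEAE window opens the day after the first KGAA injection, so a new non-serious event that starts on the first dosing day and does not later worsen is left out of the registry 'Other' AE table

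*SAP*

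**What the plan says.** SAP 6.14 sets both ends of the TEAE window in one sentence. An event qualifies if it "first occurred or worsened in severity after the date of the first injection in Study KGAA/AD07". At the other end, the onset or worsening must fall "on or prior to the date of the last visit within the treatment period". The closing date is included and the opening date is not.

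SAP 6.20 then uses the flag for the registry: "An AE is considered in the 'Other' category if it is both a TEAE and is not serious". Serious events are tabulated there regardless of TEAE status. The section also states that "AE reporting is consistent with other document disclosures, for example, the CSR, manuscripts, and so forth", and it allows 'Other' terms below 5% in every treatment group to be omitted if that threshold is chosen.

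Other date rules in the SAP treat the first dosing day as part of KGAA:

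- **6.8.2 (medical history).** A history event that worsens or "has a recurrence on or after the date of the first injection in Study KGAA" is recorded as an AE. For direct-entry patients, events on the KGAA AE form count as history only if they are on the "eCRF that occur before the date of the first injection in Study KGAA".
- **6.14 (serious events).** For parent-study patients, "SAEs that occur on or after the date of first visit to Study KGAA will be reported".
- **6.10 (medications).** "Prior medications are those medications that start and stop prior to the date of first dose of study treatment in Study KGAA".
- **6.14.1 (exposure).** Duration is the end date minus the first-dose date plus 1, so the first dosing day counts as an exposed day.

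**The concern.** The first injection is given in clinic at Baseline (SAP 5.1.1). For direct-entry patients, and for those on placebo through the end of the parent study, that visit starts the loading dose. A reaction on that day bears directly on tolerability. Under 6.14 it is not treatment-emergent, while the same reaction one day later is. Because 6.20 makes TEAE status a condition for non-serious events, the exclusion carries through to a public table.

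The SAP gives no reason for the strict bound, and its other rules place the day inside the study. That suggests a drafting slip, but a programmer who follows the text would drop the day.

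**Working it through.** The plan states no figure to reproduce, so the check applies its date rules to test cases.

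**Inputs.** D = date of first KGAA injection; L = date of last treatment-period visit; x = date of onset or of worsening.

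- SAP 6.14: TEAE if D < x ≤ L.
- SAP 6.20: 'Other' = TEAE and not serious; 'Serious' does not depend on TEAE status.
- Amended rule: TEAE if D ≤ x ≤ L.

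| Event | As written | Amended bound |
|---|---|---|
| Non-serious, starts and resolves on D | D < D is false: not a TEAE, not in 'Other' | TEAE, in 'Other' |
| Non-serious, starts on D, continues without worsening | Not a TEAE, not in 'Other' | TEAE, in 'Other' |
| Non-serious, starts on D, worsens between D+1 and L | TEAE, in 'Other' | Unchanged |
| Non-serious, starts on D+1 | TEAE, in 'Other' | Unchanged |
| Serious, starts on D | In 'Serious' | Unchanged |

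Entry to 'Other' is subject to any 5% threshold. The first two rows are the gap. The bound in 6.14 makes no distinction by route of entry, so it applies to every patient.

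**Against 6.8.2.** A history event that worsens on D is recorded as an AE with D as its start date. Under 6.14 that AE fails D < D. One section creates an AE on that day and the other does not class it as treatment-emergent. For a direct-entry patient, a new event on D is neither history (it is not before D) nor a TEAE.

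**Against 6.14.1.** Take a patient whose last treatment-period visit falls exactly at Week 100, so L = D + 100 × 7 = D + 700.

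- Exposure = (D + 700) − D + 1 = 701 days.
- TEAE window = D+1 to D+700 = 700 dates.
- Difference = 1 day, the first dosing day.
- Q2W dosing dates at Weeks 0, 2, …, 98: 98/2 + 1 = 50. The window covers 49 of them.

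These counts describe the window, not events lost.

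**Can another rule restore the event?** SAP 6.1.3 drops parent-study AEs that ended before the first KGAA dose date. An event on D does not meet that condition, so it stays in AE reporting, but the rule does not make it a TEAE. The same section reports all AEs for direct-entry patients, again without changing the TEAE condition in 6.20. No other section supplies it.

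**The case against.** The strongest reply concerns weight. Only one output is stated to use the flag. Serious events are tabulated regardless. The primary endpoint and the listings and summaries of AEs leading to discontinuation are not defined through TEAE status, nor are the AE group summaries in 6.1.3. With the 5% threshold, a rare Day 1 term might not be posted even if it were flagged. All of this stands and limits the point to one table.

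The comparison rules also serve other purposes: 6.10 classifies medications, the serious-event rule is tied to a visit, and 6.8.2 speaks of an AE rather than a TEAE. That is fair. They show that the bound is out of line with its surroundings; they do not contradict it.

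A further reply is that Baseline Day 1 is also the parent exit visit for parent-study patients (SAP 5.1.1), so a strict bound keeps findings made before the injection out of KGAA. This has force, but the strict bound also removes reactions after the injection, and it does so for direct-entry patients, who have no parent visit.

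A reader might infer three stronger things. One is that first-day reactions disappear from safety reporting altogether; 6.1.3 and the serious-event rules show otherwise. Another is that the gap affects only direct-entry patients; the bound in 6.14 applies to all. The third is that a number of missing events can be stated; the documents give no Day 1 counts.

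**Conclusion.** The point holds, with a narrow consequence. As written, a new non-serious event that starts on the first KGAA dosing day and does not later worsen is not a TEAE and is left out of the registry 'Other' table. The window is short by one date per patient. The number of events cannot be derived, and the threshold may reduce what would have been posted. The change is worth making because the omitted date is the first dosing day, the table is public and the correction is small.

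The conclusion rests on reading 6.14 literally and on 'Other' being the only output that uses the flag. The separate Program Safety Analysis Plan is not among the documents, so whether it defines TEAE differently cannot be checked.

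**What to change.** In SAP 6.14, change the lower bound to on or after the date of the first injection in Study KGAA, and add a rule for same-day events:

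- Exclude those documented as starting before the injection.
- Exclude those already recorded as parent-study AEs that did not worsen.
- Count those of unknown timing as TEAEs.

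Rerun the flag for the 'Other' table and report how many events change status. Given the consistency statement in 6.20, note any difference from the CSR approved on 22 Jan 2025.

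The cost is a short text change, one derivation flag, one table rerun and possibly an explanatory note. The downside is that some same-day events of unknown timing that in fact preceded the injection may be counted as TEAEs, mainly in parent-study patients whose Day 1 is also the parent exit visit. The revision history says that Version 3 was approved before the final database lock. The documents do not show whether the lock or a registry posting has since taken place; if a posting has, it would need correcting.
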